6.3 Bioanalytical Method

Plasma concentrations of APC-PCI will be determined using an enzyme-linked immunosorbent assay (ELISA) validated with respect to accuracy, precision, linearity, sensitivity, and specificity at Celerion, Lincoln, Nebraska. The analytical range (lower limit of quantitation [LLOQ] – upper limit of quantitation [ULOQ]) for APC-PCI is expected to be 0.02 – 1.00 ng/mL.

Blood samples for protein C will be shipped to Aronora.

6.4 Investigational Product and PD Analyte Information

6.4.1 E-WE Thrombin (APC-PCI)

E-WE thrombin is a purified protein produced by recombinant DNA technology in a bacterial (*Escherichia coli*) cell culture system. Injection of E-WE thrombin results in the temporal and selective generation of endogenous APC and subsequent escape of some of this endogenous APC into the blood circulation. *In vitro*, in the presence of phospholipid membranes, APC inactivates factor Va and factor VIIIa, resulting in a temporal prolongation of the aPTT that is observed at higher doses of E-WE thrombin.

6.5 APC-PCI Concentrations

Plasma concentrations of APC-PCI as determined at the collection times and per the bioanalytical method described in Section 6.2 and Section 6.3, respectively, will be presented graphically for all treatments (2 active dose levels and pooled placebo).

6.6 Data Summarization and Presentation

6.6.1 APC-PCI

All plasma APC-PCI concentrations and descriptive statistics will be generated using SAS® version 9.3 or higher. A concentration table will be presented for pooled placebo samples without descriptive statistics.

Plasma concentrations of APC-PCI will be listed and summarized by treatment and time points for all subjects in the PD population. Plasma concentrations will be presented with the same level of precision as received from the bioanalytical laboratory. Summary statistics, including sample size (n), arithmetic mean (Mean), standard deviation (SD), coefficient of variation (CV%), standard error of the mean (SEM), minimum, median, and maximum will be calculated for all nominal concentration time points. Excluded subjects will be included in the concentration listings, but will be excluded from the summary statistics and noted as such in the tables.

For the calculation of APC-PCI summary statistics, plasma concentrations below the limit of quantitation (BLQ) prior to the first quantifiable concentration will be set to 0 and as missing elsewhere. All BLQ values will be presented as “BLQ” in the concentration listings and footnoted accordingly.

Mean, median, and individual concentration-time profiles will be presented on linear scale. Linear mean plots will be presented with and without SD.

The level of precision for APC-PCI, URR, and Kt/Vsummary statistic will be presented as follows:

- Minimum/maximum: in same precision as in the bioanalytical/clinical laboratory database
- Mean/median: in one more level of precision than minimum/maximum
- SD/SEM: in one more level of precision than Mean/median
- n will be presented as an integer
- CV% will be presented to the nearest tenth

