	
Pharmacodynamics:
 
Plasma APC-PCI will be measured as a surrogate biomarker of drug exposure. Efficacy of antithrombotic activity will be evaluated by thrombus accumulation within the dialyzer cartridge (evaluated by visual inspection). Efficiency of HD will be assessed using blood urea nitrogen (BUN) levels before and after dialysis to determine urea removed by 4 hours of dialysis (Kt/V and URR) after E-WE thrombin active treatment versus pre-treatment and placebo.
 
Change from baseline for all PD measurements will be summarized by treatment (2 active dose levels and pooled placebo) and per timepoints using descriptive statistics.
 
Immunogenicity:
 
Development of antibodies to E-WE thrombin or wild type (WT) thrombin will be monitored using a multi-tiered approach that will include screening, confirmatory, and if applicable, antibody titer and neutralizing antibody assays.

--	---

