14.3.3 Pharmacodynamic Analyses

Placebo patients from Cohort 1 and Cohort 2 will be pooled for analysis.

Individual, mean, and median data for APC-PCI will be presented graphically for all treatments (2 active dose levels and pooled placebo).

Analysis will include assessments of drug efficacy and efficiency of HD. These will include changes in thrombus accumulation and measurement of urea removed by 4 hours of dialysis (Kt/V and URR).

The change from baseline in endpoints will be summarized by treatment (2 active dose levels and pooled placebo) and at each scheduled time point using descriptive statistics. The baseline values are any value observed from Day -8 to Day 1, prior to E-WE thrombin administration. An average of predose values may be used as baseline, as applicable. Any values after a single dose of E-WE thrombin are regarded as post-baseline values.

The change from baseline variables will be calculated as the post-baseline value minus the value at baseline.

Additional analyses may be performed as deemed necessary upon review of the data.

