14.2 Pharmacodynamic Data Summary Tables and Figures

14.2.1. Plasma APC-PCI Tables and Figures

Table 14.2.1.1.1 Plasma APC-PCI Concentrations (unit) Following Administration of 1.5 $\mu\text{g}/\text{kg}$ E-WE Thrombin – Day 1 (PD Population)

Table 14.2.1.1.2 Plasma APC-PCI Concentrations (ng/mL) Following Administration of 3.0 $\mu\text{g}/\text{kg}$ E-WE Thrombin – Day 1 (PD Population)

Table 14.2.1.1.3 Plasma APC-PCI Concentrations (ng/mL) Following Administration of Placebo – Day 1 (Pooled)

Figure 14.2.1.2.1 Arithmetic Mean (SD) Plasma APC-PCI Concentration Versus Time Profiles Following Administration of 1.5 and 3.0 $\mu\text{g}/\text{kg}$ E-WE Thrombin – Day 1 (Linear Scale) (PD Population)

Figure 14.2.1.2.2 Arithmetic Mean Plasma APC-PCI Concentration Versus Time Profiles Following Administration of 1.5 and 3.0 $\mu\text{g}/\text{kg}$ E-WE Thrombin – Day 1 (Linear Scale) (PD Population)

Figure 14.2.1.2.3 Median Plasma APC-PCI Concentration Versus Time Profiles Following Administration of 1.5 and 3.0 $\mu\text{g}/\text{kg}$ E-WE Thrombin – Day 1 (Linear Scale) (PD Population)

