10.3 Section 14 Summary Tables Shells

Page 1 of X

Table 14.1.1 Summary of Disposition Safety Population)

Disposition	Dose Level of E-WE Thrombin			Placebo (Pooled)	Overall
	1.5 µg/kg	3.0 µg/kg			
Dosed	X (XX%)	X (XX%)		X (XX%)	X (XX%)
Completed	X (XX%)	X (XX%)		X (XX%)	X (XX%)
Discontinued	X (XX%)	X (XX%)		X (XX%)	X (XX%)
<Reason 1>	X (XX%)	X (XX%)		X (XX%)	X (XX%)
<Reason 2>	X (XX%)	X (XX%)		X (XX%)	X (XX%)

Program: /CAXXXX/sas_prg/stsas/tab PROGRAMNAME.sas DDMMYYYY HH:MM

Table 14.1.2 Demographic Summary (Safety Population)

Trait	Category/ Statistics	Dose Level of E-WE Thrombin			Placebo (Pooled)	Overall
		1.5 µg/kg	3.0 µg/kg			
Sex	Male	X (XX%)	X (XX%)		X (XX%)	X (XX%)
	Female	X (XX%)	X (XX%)		X (XX%)	X (XX%)
Race	Asian	X (XX%)	X (XX%)		X (XX%)	X (XX%)
	Black or African	X (XX%)	X (XX%)		X (XX%)	X (XX%)
	American					
	White	X (XX%)	X (XX%)		X (XX%)	X (XX%)
Ethnicity	Hispanic or Latino	X (XX%)	X (XX%)		X (XX%)	X (XX%)
	Not Hispanic or Latino	X (XX%)	X (XX%)		X (XX%)	X (XX%)
Age* (yrs)	n	X	X		X	X
	Mean	XX.X	XX.X		XX.X	XX.X
	SD	X.XX	X.XX		X.XX	X.XX
	Minimum	XX	XX		XX	XX
	Median	XX.X	XX.X		XX.X	XX.X
	Maximum	XX	XX		XX	XX
Weight (kg)	n	X	X		X	X
	Mean	XX.X	XX.X		XX.X	XX.X
	SD	X.XX	X.XX		X.XX	X.XX
	Minimum	XX	XX		XX	XX
	Median	XX.X	XX.X		XX.X	XX.X
	Maximum	XX	XX		XX	XX

Programmer Note: This is just a mock table shell. Please use the race categories listed in the CRF.
 Please also include Height (cm) and BMI (kg/m²).

Note: *Age is calculated at the time of informed consent.

Program: /CAXXXX/sas_prg/stsas/tab PROGRAMNAME.sas DDMMYYYY HH:MM

Tables 14.2.1.1.1 through 14.2.1.1.3 will be in the following format:

Table 14.2.1.1.1 Plasma APC-PCI Concentrations (unit) Following Administration of 1.5 µg/kg E-WE Thrombin – Day 1 (PD Population)

Subject Number	Predose	Sample Times (hr)							
		XX	XX	XX	XX	XX	XX	XX	XX
X	BLQ	XX	XX	XX	XX	XX	XX	XX	XX
X	BLQ	XX	XX	XX	XX	XX	XX	XX	XX
X	BLQ	XX	XX	XX	XX	XX	XX	XX	XX
n	XX	XX	XX	XX	XX	XX	XX	XX	XX
Mean	XX.X	XX.X	XX.X	XX.X	XX.X	XX.X	XX.X	XX.X	XX.X
SD	XX.XX	XX.XX	XX.XX	XX.XX	XX.XX	XX.XX	XX.XX	XX.XX	XX.XX
CV%	.	XX.X	XX.X	XX.X	XX.X	XX.X	XX.X	XX.X	XX.X
SEM	XX.XX	XX.XX	XX.XX	XX.XX	XX.XX	XX.XX	XX.XX	XX.XX	XX.XX
Minimum	XX	XX	XX	XX	XX	XX	XX	XX	XX
Median	XX.X	XX.X	XX.X	XX.X	XX.X	XX.X	XX.X	XX.X	XX.X
Maximum	XX	XX	XX	XX	XX	XX	XX	XX	XX

For the calculation of summary statistics, values that are below the limit of quantitation (BLQ) of <XX> ng/mL are treated as 0 before the first quantifiable concentration and as missing elsewhere.

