. = Value missing or not reportable.

Notes for Generating the Actual Table:

- Please use CPCConcl template
- Per study design needs, the following changes are made to this table relative to Celerion standard: columns <Treatment Sequence> and <Study Period> will be removed;
- Concentrations will be presented to the same precision as in the bio data;
- Summary statistics presentation with respect to the precision of the bio data or clinical laboratory data: n = integer; Mean and Median +1; SD and SEM +2, Minimum and Maximum +0, CV% to 1 decimal;
- PK Time points are: predose (hour 0) and 0.167, 0.5, 1, 2, 4, 6, and 24 hours post E-WE Thrombin bolus dose;
- For Table 14.2.1.1.3 there will be no summary statistics.

Program: /CAXXXX/sas_prg/pksas/pk-conc-tables.sas DDMMYYYY HH:MM
Program: /CAXXXX/sas_prg/pksas/pk-conc-tables-sig.sas DDMMYYYY HH:MM
Program: /CAXXXX/sas_prg/pksas/adam_conc.sas DDMMYYYY HH:MM

Tables 14.2.2.1 will be in the following format:

Page 1 of X

Table 14.2.2.1 Summary of Clotting in Dialysis Venous Chamber Days -7 to 3 (PD Population)

Day	Time Point	1.5 µg/kg E-WE Thrombin							3.0 µg/kg E-WE Thrombin							Placebo (Pooled)						
		Category*							Category*							Category*						
		1	2	3	4	5	6	7	1	2	3	4	5	6	7	1	2	3	4	5	6	7
Day -7	Post HD	X	X	X	X	X	X	X	X	X	X	X	X	X	X	X	X	X	X	X	X	X
Day -5	Post HD	X	X	X	X	X	X	X	X	X	X	X	X	X	X	X	X	X	X	X	X	X
Day -2	Post HD	X	X	X	X	X	X	X	X	X	X	X	X	X	X	X	X	X	X	X	X	X
Day 1	Post HD	X	X	X	X	X	X	X	X	X	X	X	X	X	X	X	X	X	X	X	X	X
Day 3	Post HD	X	X	X	X	X	X	X	X	X	X	X	X	X	X	X	X	X	X	X	X	X

Note: *Category: 1 = No detectable clotting

2 = Presence of fibrinous ring or minimum clot affecting less than 5% of chamber space,

3 = Clot formation (affecting more than 5% of but less than 25% of chamber space),

4 = Clot formation (affecting more than 25% of but less than 50% of chamber space),

5 = Clot formation (affecting more than 50% of but less than 75% of chamber space),

6 = Clot formation (affecting more than 75% of chamber space),

7 = Occluded (also assess the category of clot that caused occlusion)

HD: hemodialysis

Program: /AAXXXX/ECR/sas_prg/stsas/tbl_PROGRAMNAME.sas DDMMYYYY HH:MM

Aronora, Inc.
 E-WE thrombin, Protocol EWE-19-02
 Celerion, Clinical Study Report No. CA26622

Tables 14.2.3.1 will be in the following format:

Page 1 of X

Table 14.2.3.1 Summary of Clotting in the Dialysis Filter (Safety Population)

Day	Time Point	1.5 µg/kg E-WE Thrombin						3.0 µg/kg E-WE Thrombin						Placebo (Pooled)					

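### APC-PCI summaries count the same BLQ result as 0 before dosing but as missing at 24 h, and the protocol's change-from-baseline summary, pooled placebo included, is dropped without disclosure

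*SAP*

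**What the plan says.** The BLQ rule is in SAP 6.6.1: "plasma concentrations below the limit of quantitation (BLQ) prior to the first quantifiable concentration will be set to 0 and as missing elsewhere". The footnote to the Table 14.2.1.1.x shells in SAP 10.3 repeats that such values "are treated as 0 before the first quantifiable concentration and as missing elsewhere". SAP 6.3 states that the assay range "for APC-PCI is expected to be 0.02" ng/mL at its lower end.

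For the control group, SAP 6.6.1 states: "A concentration table will be presented for pooled placebo samples without descriptive statistics". The shell note agrees: "For Table 14.2.1.1.3 there will be no summary statistics". The APC-PCI tables listed in SAP 9.2 are three concentration tables, one per group (the third is titled "Plasma APC-PCI Concentrations (ng/mL) Following Administration of Placebo"). None shows change from baseline.

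The protocol planned more. Its Section 14.3.3 says "The change from baseline in endpoints will be summarized by treatment (2 active dose levels and pooled placebo) and at each scheduled time point", and the Synopsis applies change from baseline by treatment, pooled placebo included, to every PD measurement. Protocol 14.3 allows the SAP to modify the protocol's analyses, but SAP section 8 reports that the two documents agree.

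**The concern.** Zero-then-missing treats APC-PCI like a drug with no level before dosing. It is instead a biomarker with a predose value against which later values are read, and SAP 6 uses it to show the size and duration of drug action. Under this rule zeros pull the predose mean down and dropped values push the late mean up, so the two columns a reader will compare are not on the same footing. Near the LLOQ, a group fully back at its predose level can appear still raised at 24 h.

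The first-in-human data in Protocol 8.2.2.2 make the pattern plausible on active drug: APC-PCI was detectable in every subject at 5 minutes and back at baseline by 24 h. A patient BLQ at 24 h would therefore normally have an earlier quantifiable value, which triggers the missing rule.

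A patient who is never quantifiable has no clear rule: one reading of the text gives 0 throughout, the other gives missing. This is most likely on placebo.

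The omitted summaries matter because predose is drawn before dialysis starts (SAP 6.2). Pooled placebo is the control for any effect of dialysis itself on APC-PCI, and no planned summary table makes that comparison.

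**Working it through.** The plan has no figure to reproduce here: Protocol 14.1 sets the sample size without statistical considerations. The design gives 2 × (12 + 6) = 36 patients, or 12 / 12 / 12 once placebo is pooled.

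**Inputs from the documents.** BLQ rule (SAP 6.6.1); LLOQ L = 0.02 ng/mL, expected (SAP 6.3); samples at predose, 0.167, 0.5, 1, 2, 4, 6 and 24 h (SAP 6.2); 12 patients per summary group.

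**Assumptions.** Baseline median M and the coefficients of variation (CVs), since the documents give no ESRD baseline. Values are taken as lognormal.

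**1. The rule on one profile.** The illustrative series BLQ, 0.3, 0.6, 0.5, 0.4, 0.4, 0.1, BLQ becomes 0, 0.3, 0.6, 0.5, 0.4, 0.4, 0.1, missing.

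**2. Exact ratio when nothing has changed.** Let a share p be BLQ at both predose and 24 h and quantifiable in between, and let m be the unchanged mean of the rest. Predose mean = (1 − p)m; 24 h mean = m; ratio = 1/(1 − p).

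| BLQ at both times, of 12 | Ratio 24 h / predose |
|---|---|
| 0 | 12/12 = 1.00 |
| 2 | 12/10 = 1.20 |
| 3 | 12/9 = 1.33 |
| 6 | 12/6 = 2.00 |

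With the others at 0.03 ng/mL, the means are 0.0225 against 0.030 for 3 of 12 and 0.015 against 0.030 for 6 of 12.

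**3. Reported 24 h mean against the true mean.** With σ² = ln(1 + CV²) and z = ln(L/M)/σ, the BLQ share is Φ(z) and the ratio of reported to true mean is Φ(σ − z)/(1 − Φ(z)). For M = 0.020 and CV 50%: σ = 0.472, z = 0, ratio = 0.68/0.50 = 1.36.

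| M (ng/mL) | Ratio, CV 50% / 80% | Expected quantifiable n of 12 |
|---|---|---|
| 0.015 | 1.64 / 1.80 | 3.3 / 4.1 |
| 0.020 | 1.36 / 1.52 | 6.0 / 6.0 |
| 0.03 | 1.13 / 1.25 | 9.7 / 8.6 |
| 0.05 | 1.02 / 1.08 | 11.7 / 10.8 |
| 0.1 | 1.00 / 1.01 | about 12 |

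At M = 0.010 only 0.9 / 1.9 patients are expected to be quantifiable, and no mean at all can be printed in 41% / 12% of samples, so no multiplier is claimed there.

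**4. What a change-from-predose table would show under the current rule.** This simulates 12 active patients back at their predose level at 24 h (true change 0), all quantifiable in between, with between- and within-patient CV each 30% or 50%.

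| M (ng/mL) | Mean spurious change (ng/mL) | Share of true mean |
|---|---|---|
| 0.020 | +0.006 to +0.013 | 27–54% |
| 0.03 | +0.003 to +0.007 | 9–20% |
| 0.05 | +0.000 to +0.003 | 1–4% |
| 0.1 | at most 0.0005 | negligible |

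Using 0, LLOQ/2 or LLOQ at every time point gives 0 in every case.

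Steps 2 and 4 fit together. With no within-patient variation, patients BLQ at 24 h leave the paired change and the rest show 0, although the group means still differ. With variation, a patient moving from BLQ to quantifiable counts as a full rise, while one moving the other way is dropped. That asymmetry produces the spurious change.

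**5. Protocol against SAP.** Protocol Synopsis and 14.3.3: change from baseline, two doses plus pooled placebo. SAP 6.6.1, 9.2 and 10.3: concentrations only, no change table, no placebo statistics. SAP 8: no departure reported.

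A lesser mismatch: SAP 6 and 6.5 promise graphs that include pooled placebo, while the figure titles name only the active doses. SAP 10 says the shells may be incomplete, and the individual-figure legend note points to treatment descriptions that include placebo. This is a title inconsistency, not evidence that placebo is left off the plots.

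**The case against.** The strongest reply is that the consequence rests on an unknown baseline. If ESRD patients sit well above 0.02 ng/mL, nothing happens. At an assumed median of 0.03 the spurious change (0.003 to 0.007) is smaller than the sampling SD of a 12-patient mean change (0.006 to 0.012). The peak is unaffected, and n and the individual BLQ entries are printed, so a careful reader can see what was dropped. All of this stands and limits the weight. It does not justify scoring the same result in two ways when a consistent rule costs nothing.

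Duration is also read from the samples through 6 h. The infusion ends at 4 h and Protocol 8.2.1.2 reports a 20-minute half-life for the complex, so 6 h is 120/20 = 6 half-lives later. The 24 h sample mainly confirms return to baseline. That is fair, but confirming return is exactly the reading the rule distorts.

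Step 4 concerns a table the SAP does not plan. True; it matters because restoring the protocol's table without changing the BLQ rule would import the artefact.

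Finally, the APC-PCI sentence in Protocol 14.3.3 asks only for graphs, the SAP may modify the protocol's plan, and change-from-baseline tables are also absent for clotting, URR and Kt/V. The Synopsis, however, covers all PD measurements. Permission to modify does not make the alignment statement in SAP section 8 correct, and the wider gap is a further reason to correct it.

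**Conclusion.** The concern holds. The BLQ rule makes predose and late means non-comparable and leaves never-quantifiable patients undefined. The protocol's APC-PCI change-from-baseline summary, including pooled placebo, is missing while the SAP declares alignment.

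The 1/(1 − p) ratio is exact under its stated conditions. How far it applies in this trial depends on how many patients are BLQ at 24 h, which the documents do not allow one to predict. Under the assumed distributions the distortion is material at baseline medians of about 0.015 to 0.03 ng/mL, small at 0.05 and negligible at 0.1. Confidence is high in the inconsistency and the omission, and conditional on baseline for the numerical effect. APC-PCI is a descriptive secondary biomarker with no hypothesis test, so this should be corrected but does not threaten the trial's primary conclusions.

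**What to change.** Make these changes together in SAP 6.6.1, the SAP 9 lists and the SAP 10 shells:

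- Apply one prespecified BLQ constant at all time points and in all three groups, including patients never quantifiable: for example LLOQ/2, with 0 and LLOQ as sensitivity analyses. Consistency matters more than the value chosen.
- Report the number BLQ at each time point, and show the median as BLQ when more than half the values are BLQ.
- Give Table 14.2.1.1.3 the same statistics as the active groups, and add change from predose for both doses and pooled placebo.
- Align the figure titles with SAP 6 and 6.5.

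If the sponsor prefers not to restore the summaries, SAP section 8 should state the departure and its reason. That answers the disclosure point only; the BLQ rule still needs changing.

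The cost is SAP wording and shell edits, with no new data. The drawback is that any substituted constant is arbitrary and understates spread when many values are BLQ. In the lognormal cases (CV 50% and 80%), LLOQ/2 returns 0.88 to 1.04 times the true mean at medians of 0.010 to 0.020 ng/mL, but 1.20 to 1.22 times at 0.0075 and 1.63 to 1.79 times at 0.005. At those two lowest medians, 0 returns 0.01 to 0.24 times and LLOQ 2.2 to 3.6 times, so the BLQ counts and the median rule should carry the interpretation there.

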7. SAFETY

All case report form (CRF) data will be listed by subject and chronologically by assessment time points. This will include rechecks, unscheduled assessments, and early termination.

Applicable continuous variables will be summarized using n, arithmetic mean, SD, minimum, median, and maximum. Data from subjects who received the placebo treatment will be pooled across cohorts.

The level of precision will be presented as follows: minimum/maximum in the same precision as in the database, mean/median in one more precision level than minimum/maximum, SD in one more precision level than mean/median, and n will be presented as an integer. Percentages of total frequency counts, if presented, will be reported as whole numbers.

Where individual data points are missing because of dropouts or other reasons, the data will be summarized based on reduced denominators.

7.1 Subject Discontinuation

Subjects will be summarized by number of subjects dosed, completed, and discontinued the study with discontinuation reasons by treatment (two dose levels and pooled placebo) and study overall.

7.2 Demographics

Descriptive statistics will be calculated for continuous variables (age, weight, height, and body mass index) and frequency counts will be provided for categorical variables (race, ethnicity, and sex) by treatment and overall. Age will be derived from date of birth to date of informed consent.

7.3 Adverse Events

All adverse events (AEs) occurring during this clinical trial will be coded using the Medical Dictionary for Regulatory Activities (MedDRA®), Version 21.1.

All AEs captured in the database will be listed in by-subject data listings including verbatim term, coded term, treatment, severity, relationship to study medication, and action; however, only treatment-emergent AEs (TEAEs) will be summarized.

A TEAE is defined as an AE that is starting or worsening at the time of or after study drug administration. Each TEAE will be attributed to a treatment based on the onset date and time of the AE. If the onset time of an AE is missing and the onset date is the same as the treatment dosing date, then the AE will be considered treatment emergent. If the onset date of an AE is missing, then the AE will be considered treatment emergent.

TEAEs will be tabulated by System Organ Class (SOC) and Preferred Term. Summary tables will include number of subjects reporting the AE and as percent of number of subjects dosed by treatment and overall. The number of AEs will be tabulated in a similar manner. Tables which tabulate the number of TEAEs by severity and relationship to study treatment will also be included.

Serious adverse events (SAEs), if present, will also be listed. Applicable narratives will be included in the CSR.

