A placebo arm is included in this study design in order to robustly demonstrate the safety and efficacy of E-WE thrombin while not placing the patients at unnecessary risk, as mentioned above. The primary endpoint in this study is safety, measured as the number or frequency/rate of AEs that occur during the comparable observation periods. A heparin-free inpatient HD observation period (from Day -8 to Day 1 prior to dosing) is included in the trial design to establish a baseline for the heparin-free procedure. Continuation of the heparin-free HD procedure during the subsequent trial period and inclusion of a placebo arm allows for the determination of whether an AE is drug-related or not and permits accurate assessment of the safety of the study drug. The addition of a placebo arm also removes potential bias from the interpretation of AEs by the PIs and from the reporting by the patients. The secondary endpoint for this study is efficacy of E-WE thrombin on HD which may be more clearly observed with a placebo control instead of an active control (e.g., heparin). While the placebo arm may be at the same risk of clotting within the dialysis circuit as during the pre-dosing period (Days -8 to 1), data cited above suggests that these patients will not be at higher risk for either thromboembolic or bleeding complications. Should clotting occur within the dialyzer cartridge during a HD session that results in dialyzer failure, the dialyzer cartridge will be replaced, and the patient will be closely monitored by

the PI. It is important to note that replacement of the dialyzer cartridge during HD is safe for the patient and a routine procedure in cases of dialyzer failure.

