9.2 Study Endpoints

Primary outcome measures:

- The safety and tolerability of E-WE thrombin following active treatment will be evaluated versus pre-treatment and placebo by number and severity of AEs (including HD vascular access site reactions), physical examinations, bleeding time from the HD vascular access sites, vital sign measurements, 12-lead ECGs, clinical laboratory tests, and coagulation tests.

Secondary outcome measures:

- PD of E-WE thrombin will be measured by APC-PCI and plasma APC-PCI will act as a surrogate marker for E-WE thrombin drug exposure.
- Efficacy of antithrombotic activity will be evaluated by thrombus accumulation within the dialyzer cartridge (evaluated by visual inspection) after E-WE thrombin active treatment versus pre-treatment and placebo.
- Efficiency of HD will be assessed using BUN levels before and after dialysis to determine urea removed by 4 hours of dialysis (Kt/V and URR) after E-WE thrombin active treatment versus pre-treatment and placebo.

Other outcome measures:

- Development of antibodies to E-WE thrombin or WT thrombin after drug exposure.

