13.2.8.3 Reporting

All AEs that occurred during this clinical study (i.e., before, during, and after exposure of ESRD patients to E-WE thrombin) will be recorded. This design is to improve Sponsor ability to obtain reliable initial information about drug safety yet reducing the number of study patients needed to generate useful information.

AEs and SAEs, including those related to study participation (e.g., protocol-mandated intervention), will be recorded from the time of patient check-in until study completion.

AEs will be coded using the most current Medical Dictionary for Regulatory Activities (MedDRA)[®] available at Celerion.

The PI or designee will review each event and assess its relationship to study drug (likely, probably, possibly, unlikely, or unrelated) and severity. The date and time of onset, time relationship to drug dosing, duration, and outcome of each event will be noted.

Relationship of AE:

The relationship of each AE to the study drug will be assessed using the following definitions:

Unrelated	
 ▪ The adverse event must clearly be caused by the participant's clinical state, or the study procedure/conditions ▪ Definitely not related to drug ▪ Temporal sequence of an adverse event onset relative to administration of drug not reasonable ▪ Another obvious cause of an adverse event
Unlikely	
 ▪ Time sequence is unreasonable ▪ There is another more likely cause for an adverse event
Possibly	
 ▪ Corresponds to what is known about the drug ▪ Time sequence is reasonable ▪ Could have been due to another equally, likely cause
Probably	
 ▪ Is a known effect of the drug ▪ Time sequence from taking drug is reasonable ▪ Ceases on stopping the drug ▪ Cannot be reasonably explained by the known characteristics of the participant's clinical state
Likely	
 ▪ Is a known effect of the drug (e.g. listed in IB) ▪ Time sequence from administering drug is reasonable ▪ Event stops upon stopping drug and returns upon restarting drug

Severity of AE:

Severity rating used during the study will be based on the toxicity grading scale tables present in the FDA (Center for Biologics Evaluation and Research) toxicity grading scale for healthy volunteers 4-point severity scale (Grade 1, 2, 3 and 4) [11].

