2.2 Endpoints

Primary outcome measures:

- The safety and tolerability of E-WE thrombin following administration of the active treatment will be evaluated versus pre-treatment and placebo by number and severity of AEs (including HD vascular access site reactions), physical examinations, bleeding time from the HD vascular access sites, vital sign measurements, 12-lead ECGs, clinical laboratory tests, and coagulation tests.

Secondary outcome measures:

- Pharmacodynamics of E-WE thrombin will be measured by APC-PCI and plasma APC-PCI will act as a surrogate marker for E-WE thrombin drug exposure.
- Efficacy of antithrombotic activity will be evaluated by thrombus accumulation within the dialyzer cartridge (evaluated by visual inspection) after E-WE thrombin active treatment versus pre-treatment and placebo.
- Efficiency of HD will be assessed using BUN levels before and after dialysis to determine urea removed by 4 hours of dialysis (Kt/V and URR) after E-WE thrombin active treatment versus pre-treatment and placebo.

Other outcome measures:

- Development of antibodies to E-WE thrombin or WT thrombin after drug exposure.

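### The endpoint judges AEs against pre-treatment as well as placebo, but the SAP summarizes only TEAEs, so no table delivers the run-in AE comparison

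*SAP*

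**What the plan says.** **Endpoint.** Protocol 9.2 states that safety "will be evaluated versus pre-treatment and placebo by number and severity of AEs". SAP 2.2 repeats this: "following administration of the active treatment will be evaluated versus pre-treatment and placebo by number and severity of AEs".

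**Design rationale.** Protocol 8.3.1 describes the primary endpoint as safety, "measured as the number or frequency/rate of AEs that occur during the comparable observation periods". It says the inpatient period from Day -8 to dosing "is included in the trial design to establish a baseline for the heparin-free procedure". Protocol 13.2.8.3 adds: "All AEs that occurred during this clinical study (i.e., before, during, and after exposure of ESRD patients to E-WE thrombin) will be recorded". It continues: "This design is to improve Sponsor ability to obtain reliable initial information about drug safety yet reducing the number of study patients needed".

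**Analysis.** SAP 7.3 puts all AEs in by-patient listings, but for tabulation "however, only treatment-emergent AEs (TEAEs) will be summarized". A TEAE is any AE that starts or worsens at or after dosing; no end date or sub-period is given. SAP 7.3 also says: "Each TEAE will be attributed to a treatment based on the onset date and time of the AE". In-text Table 12-1 and Tables 14.3.1.1 to 14.3.1.3 are laid out by treatment, with no run-in row or column. Protocol 14.3.1 likewise names only TEAEs for the AE summary.

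**The concern.** Number and severity of AEs are part of the primary outcome, and pre-treatment is one of the two comparators named for them. Other parts of the same outcome do show the run-in: the shells for bleeding time, vital signs and coagulation include the run-in days. AEs do not.

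This matters more than usual here. There are 12 patients per dose level and 12 on pooled placebo, and Protocol 14.1 says the number was chosen without statistical considerations. The run-in supplies most of the drug-free inpatient AE experience: 36 × 8 = 288 patient-days, against 12 × 2 = 24 for pooled placebo from dosing to Day 3. As planned, a reader who wants the pre-treatment comparison must count run-in events by hand from a listing. The only tabulated figure to set beside that count is a TEAE total gathered over a different length of time and in a different setting.

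**Working it through.** The plan states no AE rate, power or alpha, so there is no figure to reproduce. The check is of which comparisons the tables deliver, then of whether the TEAE window could stand in for the missing one.

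**Step 1: coverage**

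| Comparison named in Protocol 9.2 and SAP 2.2 | Where AEs are tabulated |
|---|---|
| Active versus placebo | Tables 12-1 and 14.3.1.1 to 14.3.1.3 |
| Active versus pre-treatment | None; listings only |

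**Step 2: window lengths.** Protocol 10.1 places Day -8 eight days before dosing on Day 1, so there is no Day 0. Confinement ends on Day 3 and follow-up is Day 14 ± 2 (Protocol 10.1.1).

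- Run-in: 8 days, all inpatient.
- TEAE window, elapsed from dosing: 14 − 1 = 13 days (12 − 1 = 11 to 16 − 1 = 15).
- Dosing to Day 3: 3 − 1 = 2 days.
- After discharge: 14 − 3 = 11 days (9 to 13).
- Share of the TEAE window after discharge: 11/13 = 85% (9/11 = 82% to 13/15 = 87%).

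**Step 3: length ratio, TEAE window to run-in**

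- Elapsed time: 13/8 = 1.63 (11/8 = 1.38 to 15/8 = 1.88).
- Calendar days, counting Day 1 and the visit day in full: 14/8 = 1.75 (12/8 = 1.5 to 16/8 = 2.0).
- Across both conventions: about 1.4 to 2.0.

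This would be the ratio of counts under a constant AE rate, equal capture and no drug effect.

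**Step 4: ascertainment.** Protocol 13.2.8.2 has patients questioned daily while confined and then at the follow-up visit. The longer window raises the TEAE count; sparser questioning may lower it. The net direction cannot be fixed from the documents.

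**Step 5: HD sessions** (Flow Chart, note e). Run-in has three (Days -7, -5, -2), or 3/8 = 0.375 per day. Dosing to Day 3 has two (Days 1 and 3), or 2/2 = 1.0 per day by elapsed time, 2.67 times as dense. A per-day rate alone would therefore mislead if AEs cluster around dialysis.

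**Step 6: what the split can show.** Patient-days per active arm (n = 12) are 12 × 8 = 96 in run-in and 12 × 2 = 24 from dosing to Day 3. The documents give no AE rate; assume 0.02 to 0.10 per patient-day.

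- Run-in: 96 × 0.02 = 1.9 to 96 × 0.10 = 9.6 events expected.
- Dosing to Day 3: 24 × 0.02 = 0.5 to 24 × 0.10 = 2.4 events expected.
- Upper bound after zero events in 24 patient-days (one-sided 95%): −ln(0.05)/24 = 2.996/24 = 0.125 per patient-day.

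**The case against.** The strongest reply is that the SAP follows the protocol's own analysis text. Protocol 14.3.1 specifies TEAEs for AEs and attaches the explicit pre-treatment comparison to bleeding time. Placebo is the cleaner control, and Protocol 8.3.1 relies on it for judging drug-relatedness. Run-in AEs are listed with onset times, severity and a treatment-emergent flag, so the comparison could be rebuilt.

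Much of this stands. SAP 8's statement of alignment is accurate for the protocol's analysis section; the mismatch is with the endpoint and lies in both documents. But the endpoint names both comparators, and neither document withdraws one for AEs. The listings are also an incomplete fallback. They are titled for the Safety Population, which holds dosed patients only, while Protocol 11.3 and 13.3 allow discontinuation in run-in for repeated clotting and say those patients' available data will be analyzed.

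It is also fair to say that run-in versus post-dose confinement is not like-for-like. Graded access-site assessment is scheduled once before dosing and three times after (SAP 7.10), although Flow Chart note i has sites checked for reactions after every session. Day 1 adds a post-dose ECG, an abbreviated examination and 1-hour vital signs. Patients who clot may already have left. This limits the comparison and has to be shown with it.

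A reader might go further and infer that the plan inflates drug harm by the ratio in Step 3. The documents do not support that. Neither plans to set the TEAE total beside a run-in count, the figure changes with day counting, and sparser questioning works the other way. The follow-up visit also asks about the whole interval since the last visit, so events after discharge are not simply lost.

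**Conclusion.** The point holds as a gap between endpoint and analysis: the pre-treatment comparison of AE number and severity is named as part of the primary outcome, and no planned table delivers it. The TEAE total cannot substitute, since it spans about 13 days (11 to 15), some 85% of them after discharge, against 8 inpatient days.

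A reader might infer that the main safety comparison is compromised. It is not. Active versus placebo is randomized and blinded, and all arms share the same TEAE window. Nor are dosed patients' run-in data lost, since they are collected and listed. Heparin does not explain the difference between windows either, because exclusion criterion 2 allows it only until check-in.

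The window lengths rest on the visit schedule, because SAP 7.3 gives no end date for TEAEs. The event expectations rest on assumed rates. This is worth correcting but does not threaten the study's validity.

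**What to change.** In SAP 7.3, add one descriptive table of AEs (patients, events, severity) by treatment and overall, in three windows: check-in to dosing; dosing to Day 3 discharge; discharge to follow-up.

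- Give events per patient-day from actual elapsed time and, for the first two windows, per HD session.
- Use the first two windows for the pre-treatment comparison. Keep the overall TEAE table for active versus placebo.
- Report access-site reactions and findings from assessments scheduled only after dosing separately, or footnote the unequal schedule.
- Show AEs with missing onset dates in the overall TEAE table only. SAP 7.3 makes them treatment-emergent, but they cannot be placed in a window.
- Show AEs of patients withdrawn before dosing in a separate column or listing. Randomization numbers are assigned at dosing (Protocol 12.3), so these patients have no treatment group.

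The cost is one table from onset dates and times already recorded, with no new visits or samples. The drawback is small counts, as Step 6 shows, so the table should be labelled descriptive and carry no test.
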